5.1. Inclusion Criteria

Each potential participant must satisfy all of the following criteria to be enrolled in the study:

1. Male or female, 18 to 65 years old (inclusive).
2. Has a confirmed clinical diagnosis of UC at least 3 months before screening.
3. Has moderately to severely active UC, defined as a baseline (Week 0) Mayo score of 6 to 12, inclusive, using the Mayo endoscopy subscore obtained during the central review of the video endoscopy.
4. Has a screening endoscopy with ≥ 2 endoscopy subscore of the Mayo score as obtained during the central review of the video endoscopy.

Concomitant or previous medical therapies received

5. Must be naïve to TNF antagonists and have a prior or current UC medication history that includes at least 1 of the following:
 - a. Inadequate response to or failure to tolerate current treatment with oral corticosteroids or immunomodulators (6-MP or AZA) as defined in Appendix 2 (Section 10.2).

OR

 - b. History of failure to respond to, or tolerate, at least 1 of the following therapies: oral or IV corticosteroids or immunomodulators (6-MP or AZA) as defined in Appendix 2 (Section 10.2).

OR

 - c. History of corticosteroid dependence (ie, an inability to successfully taper corticosteroids without a return of the symptoms of UC) as defined in Appendix 2 (Section 10.2).
6. Before the first administration of study intervention, the following conditions must be met:
 - a. If receiving oral 5-aminosalicylic acid (5-ASA) compounds, the dose must have been stable for at least 2 weeks.
 - b. If receiving oral corticosteroids other than budesonide or beclomethasone dipropionate, the dose must be ≤ 20 mg/day prednisone or its equivalent and must have been stable for at least 2 weeks.

- c. If receiving budesonide or beclomethasone dipropionate, the dose must have been stable for at least 2 weeks.
 - d. If oral 5-ASA compounds or oral corticosteroids have been recently discontinued, they must have been stopped for at least 2 weeks.
7. The following medications/therapies must have been discontinued before the first administration of study intervention:
 - a. Immunomodulators (6-MP, AZA, or MTX) for at least 2 weeks.
 - b. Vedolizumab for at least 18 weeks.
 - c. Tofacitinib and other inhibitors of JAKs for at least 4 weeks or 5 half-lives, whichever is longer.
 - d. Cyclosporine, mycophenolate mofetil, tacrolimus, or sirolimus for at least 4 weeks.
 - e. 6-thioguanine must have been discontinued for at least 4 weeks.

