 - c. The 48 hours after the use of antimotility agents (ie, diphenoxylate hydrochloride with atropine sulfate, loperamide, or other opioids).
 - d. The 48 hours immediately following a colonoscopy.
2. The physician's global assessment.
3. The results of a sigmoidoscopy or colonoscopy.

The **partial Mayo score** is the Mayo score without the endoscopy subscore and ranges from 0 to 9 points.

If 1 or more of the 4 Mayo subscores is missing at a specific visit, but not all 4 subscores are missing, the last available Mayo subscore will be carried forward to compute a full Mayo score and a partial Mayo score at that visit. If all 4 subscores are missing at a specific visit, the Mayo score and partial Mayo score will be considered missing at that visit.

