9.4.1.2. Primary Endpoint Analyses

The primary endpoint is clinical response at Week 12 defined as a decrease from baseline in the Mayo score $\geq 30\%$ and ≥ 3 points with either a decrease in RBS ≥ 1 or a RBS of 0 or 1. The endoscopy subscore will be based on the final reported endoscopy subscore.

Participants who have a colectomy or ostomy, or have protocol-prohibited medication changes (to be detailed in the SAP), or who have discontinued study intervention due to unsatisfactory therapeutic effect or an AE of worsening UC, before the Week 12 visit will be considered not to be in clinical response at Week 12, regardless of the actual Mayo score.

Participants with a missing Mayo score (ie, all 4 Mayo subscores are missing) or who do not return for evaluation at Week 12 will be considered not to be in clinical response at Week 12.

For testing of the primary endpoint, the efficacy of combination therapy versus each monotherapy will be compared. For both statistical comparisons of the primary endpoint, a CMH chi-square test stratified by concomitant use of corticosteroids at baseline (Y/N) will be used. The testing will be done simultaneously at the 1-sided 0.1 level of significance for each comparison.

The study will be considered positive if the combination therapy group is significantly different from both monotherapy groups for the primary endpoint.

To examine the robustness of the primary endpoint analysis, sensitivity analyses of the primary endpoint will be conducted using different missing data approaches; these analyses will be described in the SAP.

Subgroup analyses of the primary endpoint will be performed based on demographic and baseline disease characteristics, and baseline concomitant UC medication use and history of UC-related medications. Additional subgroup analyses of other endpoints (eg, clinical remission) may be considered and will be described in the SAP.

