5.3.1. Definition

Clinical response: A decrease from baseline in the Mayo score (Section 5.3.1.1) $\geq 30\%$ and ≥ 3 points, with either a decrease in the rectal bleeding subscore (RBS) ≥ 1 or a RBS of 0 or 1.

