5.3.1.1. Mayo Score, Partial Mayo Score, and Modified Mayo Score

The **Mayo score** was developed from the criteria of Truelove and Witts¹⁴ for mild, moderate, and severe UC and from the criteria of Baron et al² for grading endoscopic appearance. The Mayo score consists of the following 4 subscores:

- Stool frequency
- Rectal bleeding
- Findings of endoscopy
- Physician's global assessment (PGA)

Each subscore is rated on a scale from 0 to 3, indicating normal to severe activity, as defined in Attachment 1.

The **Mayo score** is calculated as the sum of the 4 subscores (stool frequency, rectal bleeding, PGA, and endoscopy findings) and ranges from 0 to 12 points. A score of 3 to 5 points indicates mildly active disease, a score of 6 to 10 points indicates moderately active disease, and a score of 11 to 12 points indicates severely active disease.

The **partial Mayo score**, which is the Mayo score without taking into account the findings of endoscopy, is calculated as the sum of stool frequency, rectal bleeding, and PGA subscores, and may take on values from 0 to 9.

The **modified Mayo score**, which is the Mayo score without the PGA subscore, is calculated as the sum of the stool frequency, rectal bleeding, and endoscopy subscores, and may take on values from 0 to 9.

Due to the requirement for endoscopy findings for the evaluation of the Mayo score, it is not feasible to evaluate the Mayo score at each scheduled visit in the study. Therefore, the Mayo score will be evaluated at Weeks 0, 12 and 38, and the partial Mayo score will be evaluated at the other

study visits. The modified Mayo score can be derived from the Mayo score and is not a separate evaluation.

Mayo Rectal Bleeding and Stool Frequency Subscores

The eCRFs capture seven days of rectal bleeding data and the number of stools per day prior to each visit at which the Mayo score or partial Mayo score is collected. Data from 3 of these 7 days are used to calculate the Mayo rectal bleeding and stool frequency subscores; sites are instructed to check the boxes next to the 3 days which are used (see [below](#) for information on what days the sites are instructed to use).

The Mayo rectal bleeding subscore is calculated as the average rectal bleeding number for the three days based on the criteria in Attachment 1.

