5.3.3. Analysis Methods for the Primary Estimand (Estimand 1)

5.3.3.1. Main Estimator (Analysis) for the Primary Estimand

The primary endpoint, defined in Section 5.3.1, will be analyzed based on the Primary Estimand (Section 5.3.2). After accounting for the ICEs for the primary estimand (Estimand 1), participants who are missing any or all of the Mayo subscores that comprise the primary endpoint at Week 12 will be considered not to be in clinical response at Week 12 (i.e. nonresponder imputation).

In the primary analysis, data from all participants in the FAS (Section 2.2.2) will be analyzed according to the randomized study intervention regardless of the study intervention they actually received. The treatment difference between combination therapy versus each monotherapy will be tested using a 2-sided CMH chi-square test stratified by corticosteroid use at baseline (yes, no) at the 0.2 significance level. The magnitude of the treatment difference will be estimated by the difference in the proportion of participants achieving clinical response at Week 12 between the combination therapy group and each monotherapy group with a 2-sided 80% confidence interval (CI) calculated based on Wald statistic.

The study will be considered positive if the combination therapy group is significantly different from both monotherapy groups at the 2-sided significance level of 0.2 for the primary endpoint.

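### SAP 5.3.3.1 counts any missing Week 12 Mayo subscore as non-response, an unflagged change from the protocol that also fails some participants whose response is already certain

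*SAP*

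**What the plan says.** **Protocol.** Section 8.1.1 says that when one to three of the four subscores are missing at a visit, "the last available Mayo subscore will be carried forward to compute a full Mayo score and a partial Mayo score at that visit". The score is missing only in the extreme case: "If all 4 subscores are missing at a specific visit, the Mayo score and partial Mayo score will be considered missing at that visit". Section 9.4.1.2 applies this to the primary endpoint. Non-response for missing data is assigned to "Participants with a missing Mayo score (ie, all 4 Mayo subscores are missing) or who do not return for evaluation at Week 12".

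**SAP.** After the intercurrent events (ICEs) are applied, section 5.3.3.1 assigns non-response to "participants who are missing any or all of the Mayo subscores that comprise the primary endpoint at Week 12". The SAP contains no subscore carry-forward rule and does not say that one has been dropped. It does have an endoscopy fallback in 5.3.1.1 (final reported score, then first central read, then local read), so the endoscopy subscore is missing only if no read exists.

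**Response definition.** SAP 5.3.1 requires a fall in the Mayo score of at least 30% and at least 3 points, "with either a decrease in the rectal bleeding subscore (RBS) ≥ 1 or a RBS of 0 or 1". On the range, SAP 5.3.1.1 states: "Each subscore is rated on a scale from 0 to 3, indicating normal to severe activity".

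**The concern.** The two documents can classify the same participant in opposite ways on the primary endpoint, and nothing in the SAP tells the reader that the rule changed.

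Separately, the SAP rule is not always a cautious guess about an unknown outcome. Where the observed subscores already settle the matter, it records a known response as a failure. If such cases are spread evenly over the arms, the arm with most responders loses most, so the difference shrinks. A missed Week 12 endoscopy is foreseeable: SAP 5.5 plans tables of missing endoscopy subscores by reason, including COVID-19.

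**Working it through.** **1. The plan's power figure.** Inputs from Protocol 9.2: 70 per group, one-sided 0.1 per comparison, response 55% / 55% / 75%. Exact binomial enumeration of the probability that the combination beats both monotherapies (pooled chi-square, no continuity correction) gives 81.4%; the plan's table gives 81%. The other five rows reproduce as well (79.2, 65.8, 69.1, 89.9 and 85.4% against 79, 66, 69, 90 and 85%).

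**2. One participant.** Baseline stool 2, bleeding 2, PGA 2, endoscopy 3: Mayo 9. Week 12 stool 0, bleeding 0, PGA 0, endoscopy missing. The Week 12 score is at most 0 + 0 + 0 + 3 = 3, a fall of at least 9 - 3 = 6 points (6/9 = 67%), with bleeding 0. The definition is met for every possible endoscopy value. Carrying the baseline endoscopy forward gives a responder; the SAP gives a non-responder.

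**3. General condition, endoscopy missing.** The required fall is the larger of 3 points and 30% of baseline, in whole points. With endoscopy at its worst value, response is certain if the Week 12 partial Mayo score is at most baseline - required fall - 3 and the bleeding condition holds.

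| Baseline Mayo | 6 | 7 | 8 | 9 | 10 | 11 | 12 |
|---|---|---|---|---|---|---|---|
| Required fall | 3 | 3 | 3 | 3 | 3 | 4 | 4 |
| Largest Week 12 partial Mayo | 0 | 1 | 2 | 3 | 4 | 4 | 5 |

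**4. Which missing subscores matter.** There are 98 eligible baseline profiles (Mayo 6-12, endoscopy 2 or 3), and 98 x 64 = 6272 combinations with the three observed Week 12 subscores. Response is certain in 985 of 6272 when endoscopy, PGA or stool frequency is the missing one, and in 0 of 6272 when rectal bleeding is missing. Stool frequency and bleeding come from the same diary days (SAP 5.3.1.1), so they tend to be missing together; then no case is certain. The practical cases are a missing endoscopy or a missing PGA. With endoscopy missing, baseline carry-forward credits 1245 combinations: all 985 certain ones and 1245 - 985 = 260 that are not certain.

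**5. Share of responder patterns that are certain.** Counting complete Week 12 patterns with no subscore above baseline, 4510 meet the response definition. Setting endoscopy to 3 leaves 2970 (65.9%) still responding; setting PGA to 3 leaves 59.8%; carrying baseline endoscopy forward leaves 77.3%. If worsening of individual subscores is allowed, the share with endoscopy set to 3 is 52%. These are unweighted pattern counts, not patient frequencies.

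**6. Effect on the trial.** Let r be the share of each arm lacking only endoscopy, unrelated to arm or outcome. The documents give no value, so r is assumed. The share of responders recoded as failures is m = 0.66r. Each response rate becomes p(1 - m), and the difference becomes 20(1 - m) points.

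| r (assumed) | m | Loss in difference (points) | Power |
|---|---|---|---|
| 0 | 0 | 0 | 81.4% |
| 1% | 0.66% | 0.1 | 80.6% |
| 2% | 1.32% | 0.3 | 79.8% |
| 5% | 3.3% | 0.7 | 77.5% |
| 10% | 6.6% | 1.3 | 73.9% |

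At 52% in place of 66%, the loss at r = 10% is 20 x 0.052 = 1.0 point.

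**The case against.** - **Non-responder imputation is a deliberate, pre-specified choice.** Protocol section 9 leaves details to the SAP, and the SAP uses the same approach for remission and the other binary endpoints. This stands as far as it goes: the SAP may tighten the rule. But Protocol 9.4.1.2 states its own rule in full, and replacing it should be declared.
- **Other planned analyses cover the case.** The tipping-point analysis (SAP 5.3.3.3) runs every assignment of the missing outcomes, so it includes the scenario in which these participants are responders. Estimand 3 imputes single subscores and keeps the observed ones. Both points are true. The tipping-point analysis, however, does not identify which scenario is the determined one, and Estimand 3 also treats every intercurrent event as hypothetical, so it answers a different question. Neither corrects the primary result.
- **Few participants are affected.** The endoscopy read fallback narrows the main case, and SAP 5.3.3.3 expects a very small percentage of missing data. This stands and limits the size of the point.
- **The bias is conservative for a superiority claim.** Also true, under missingness unrelated to arm and outcome.

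A reader might infer that any single missing subscore produces a false failure. It does not: with rectal bleeding missing, response is never certain. A reader might also infer that the protocol's carry-forward is therefore the right rule. The enumeration does not support that, since carry-forward also credits patterns in which response is uncertain.

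**Conclusion.** The point holds in two parts. The protocol and SAP give different primary-endpoint rules for partly missing Mayo data, and the SAP does not say so. The SAP rule also misclassifies participants whose response is fixed by what was observed, in practice those lacking only PGA or only endoscopy with no read of any kind.

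The likely effect is small: about 0.1 to 1.3 points off a 20-point difference, and power of 80.6% down to 73.9% against 81.4%, for 1% to 10% lacking only endoscopy. These figures rest on assumed missingness rates, the unweighted 66% share, equal missingness across arms, and the plan's 55/55/75% as true rates. It is tempting to read this as a material bias in the primary result. The documents do not support that, because they give no rate of partial missingness and expect little. The case for the change is that a stated rule gives a wrong answer for identifiable participants and is cheap to correct.

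**What to change.** In SAP 5.3.3.1: if some but not all Week 12 subscores are missing and no ICE of categories 1-3 has occurred, set each missing subscore to 3; score response if the definition is still met, otherwise non-response. State that this replaces the carry-forward rule of Protocol 8.1.1 and 9.4.1.2 for the primary endpoint. In 5.3.3.3, limit the tipping-point analysis to participants whose status remains undetermined. Settle this before the Week 12 database lock, when the primary endpoint is analyzed.

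The cost is a few sentences and a little programming. The fill adds no missing-data assumption, because it credits only responses that hold at the worst value. Applied to remission it would change nothing, since a subscore of 3 rules remission out. The downside is a small departure from blanket non-responder imputation, and the rule remains stricter than the protocol's carry-forward, so some participants would still be classified differently from Protocol 8.1.1. That is why the replacement must be stated.

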9.2. Sample Size Determination

A sample size of 210 participants (70 per intervention group) was determined by the power to detect a significant difference in the proportion of participants in clinical response at Week 12 (primary endpoint) between the combination therapy and both monotherapies using a 1-sided chi-square test with 0.1 significance level for each comparison. The study is sized such that the combination therapy has approximately 80% power (based on simulations) to achieve both comparisons to monotherapy for the primary endpoint.

The assumptions for the sample size calculations were based on data from the past golimumab programs conducted by the sponsor in participants with UC who were naïve to biologic therapy. The proportion of participants in clinical response at Week 12 is expected to be 55% for golimumab compared to 51% observed at Week 6 in study C0524T17 (PURSUIT), as the PURSUIT program suggested that the response rate might increase slightly with further treatment. This was also confirmed in study CNTO148UCO2001 (PROgECT).⁶⁰ The tested dose of guselkumab is assumed to have the same clinical response rate as golimumab at Week 12. The proportion of participants in clinical response at Week 12 is assumed to be 75% for the combination therapy, which is based on the additive effect from both monotherapies (20% improvement from each monotherapy relative to a historical placebo response of 35%). The different combinations of clinical response rate assumptions and associated power are displayed in [Table 4](#).

Golimumab (n=70)	Guselkumab (n=70)	Combination Therapy (n=70)	Power
50%	50%	70%	79%
50%	55%	70%	66%
55%	60%	75%	69%
55%	55%	75%	81%
55%	60%	80%	90%
60%	60%	80%	85%

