1.2. Trial Design

[figure not shown]
This is a Phase 2a, randomized, double-blind, active-controlled, parallel-group, multicenter, interventional proof-of-concept (POC) clinical study designed to evaluate the efficacy and safety of combination therapy with guselkumab and golimumab in adults with moderately to severely active UC. The target population is men or women 18 to 65 years old with moderately to severely active UC, as defined by a Mayo score of 6 to 12, inclusive, at baseline, including an endoscopy subscore ≥ 2 as obtained during the central review of the video endoscopy. Participants must be naïve to tumor necrosis factor (TNF) antagonists and have failed or not tolerated conventional therapy with oral or intravenous (IV) corticosteroids or immunomodulators (6-mercaptopurine [6-MP] or azathioprine [AZA]).

This study will consist of 2 distinct phases: a 12-week **combination comparison phase** followed by a 26-week **monotherapy phase**. At Week 0, a target of 210 participants will be randomized in a 1:1:1 ratio to either combination therapy with guselkumab and golimumab, guselkumab monotherapy, or golimumab monotherapy, stratified by corticosteroid use at baseline (yes, no). Participants randomized to combination therapy will receive guselkumab monotherapy after Week 12. Participants randomized to a monotherapy group will continue on their originally randomized monotherapy after Week 12. The combination therapy arm will employ the same dose regimens of guselkumab and golimumab being used in the respective monotherapy intervention groups to facilitate scientific interpretation of the results. The following is a description of the 3 intervention groups:

- **Combination therapy (N = 70):** guselkumab 200 mg IV and golimumab 200 mg subcutaneous (SC) at Week 0; golimumab 100 mg SC at Weeks 2, 6, and 10; guselkumab 200 mg IV at Weeks 4 and 8 followed by guselkumab 100 mg SC q8w
- **Guselkumab monotherapy (N = 70):** guselkumab 200 mg IV at Weeks 0, 4, and 8 followed by guselkumab 100 mg SC q8w
- **Golimumab monotherapy (N = 70):** golimumab 200 mg SC injection at Week 0, followed by golimumab 100 mg at Week 2 and then golimumab 100 mg every 4 weeks (q4w)

In addition, placebo administrations (IV or SC) will be given, as appropriate, to maintain blinding throughout the duration of the study. Refer to Protocol Section 6 for additional details. A diagram of the study design is provided in [Figure 1](#).

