1.4. Sample Size Justification

A sample size of 210 participants (70 per intervention group) was determined by the power to detect a significant difference in the proportion of participants in clinical response at Week 12 (primary endpoint) between the combination therapy and both monotherapies using a 1-sided chi-square test with 0.1 significance level for each comparison. The study is sized such that the

combination therapy has approximately 80% power (based on simulations) to achieve both comparisons to monotherapy for the primary endpoint.

The assumptions for the sample size calculations were based on data from the past golimumab programs conducted by the sponsor in participants with UC who were naïve to biologic therapy. The proportion of participants in clinical response at Week 12 is expected to be 55% for golimumab compared to 51% observed at Week 6 in study C0524T17 (PURSUIT), as the PURSUIT program suggested that the response rate might increase slightly with further treatment. This was also confirmed in study CNTO148UCO2001 (PROgECT)¹³. The tested dose of guselkumab is assumed to have the same clinical response rate as golimumab at Week 12. The proportion of participants in clinical response at Week 12 is assumed to be 75% for the combination therapy, which is based on the additive effect from both monotherapies (20% improvement from each monotherapy relative to a historical placebo response of 35%). The different combinations of clinical response rate assumptions and associated power are displayed in [Table 1](#).

Golimumab (n=70)	Guselkumab (n=70)	Combination Therapy (n=70)	Power
50%	50%	70%	79%
50%	55%	70%	66%
55%	60%	75%	69%
55%	55%	75%	81%
55%	60%	80%	90%
60%	60%	80%	85%

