5.2. Analysis Specifications

5.2.1. Level of Significance

A 2-sided significance level of 0.2 (equivalent to the 1-sided 0.1 level specified in the protocol) will be used for all hypothesis testing and no adjustments for multiple comparisons will be made. Nominal p-values will be presented.

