5.4.3. Analysis Methods for the Main Estimand (Estimand 4)

5.4.3.1. Main Estimator (Analysis) for the Main Estimand

The major secondary endpoint will be analyzed based on the Main Estimand (Section 5.4.2). After accounting for the ICEs for the main estimand, participants who have a missing clinical remission status at Week 12 will be considered not to be in clinical remission at Week 12 (i.e. nonresponder imputation).

In this analysis for the major secondary endpoint, data from all participants in the FAS will be analyzed according to the randomized study intervention regardless of the study intervention they actually received. The treatment difference between combination therapy versus each monotherapy will be tested using a CMH chi-square test stratified by corticosteroid use at baseline (yes, no). The magnitude of the treatment difference will be estimated by the difference in the proportion of participants achieving clinical remission at Week 12 between combination therapy and each monotherapy with a 2-sided 80% CI calculated based on Wald statistic.

The testing of the major secondary endpoints will occur at a 2-sided significance level of 0.2 regardless of the significance of the primary endpoint. No adjustment for multiple comparisons will be made and nominal p-values will be presented.

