5.5.3. Estimators (Analyses) for Estimands

Unless otherwise specified, the other endpoints presented in Section 5.5 will be analyzed based on the FAS (Section 2.2.2) according to randomized study intervention regardless of the study intervention actually received.

Descriptive statistics (i.e., mean, median, SD, IQ range, minimum, and maximum) will be used to summarize continuous endpoints and counts and percentages will be used to summarize binary endpoints by visit.

Treatment comparisons between combination therapy versus each monotherapy will be performed by visit through Week 38. All statistical testing will be performed at the 2-sided significance level of 0.2. No adjustment for multiple comparisons will be made for these other endpoints. Nominal p-values will be presented.

Binary Endpoints

After accounting for the ICEs, participants with missing status for a binary endpoint will be considered not to have achieved the associated binary endpoint (i.e. nonresponder imputation).

Binary endpoints will be summarized with the number and frequency of participants who achieve the endpoint by treatment group. Treatment comparisons (combination therapy versus each monotherapy) will be performed using analyses suitable for categorical data (e.g., a CMH chi-square test stratified by corticosteroid use at baseline, as appropriate) to compare the proportion of participants achieving the endpoints. In case of rare events, the Fisher's exact test will be used for treatment comparisons.

Continuous Endpoints

For continuous endpoints that are assessed only at one post-baseline visit (e.g., change from baseline in Mayo score and change from baseline in modified Mayo score at the Week 12 DBL), the missing data after accounting for ICEs will be imputed by the MI methods as described in [Table 3](#). The MI will be performed on each Mayo subscore with missing data and then the Mayo scores will be derived from such imputed subscores. These endpoints will be compared between combination therapy versus each monotherapy using an analysis of covariance (ANCOVA) with treatment group, corticosteroid use at baseline (yes, no), and baseline score as the explanatory factors.

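### The risk differences for Week 12 response and remission are reported without adjustment for baseline severity, so a modest gain in precision may be forgone

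*SAP*

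**What the plan says.** - **Tests.** The primary comparison is a CMH test "stratified by corticosteroid use at baseline (yes, no) at the 0.2 significance level" (SAP 5.3.3.1). Remission is "tested using a CMH chi-square test stratified by corticosteroid use at baseline (yes, no") (SAP 5.4.3.1). Corticosteroid use is the only randomisation stratum (Protocol 6.3, SAP 1.5).
- **Estimates.** Both sections report a difference in proportions with an 80% Wald interval. Neither says that the interval takes account of any factor, including corticosteroid use.
- **Baseline severity.** Entry requires a Mayo score of 6 to 12 and an endoscopy subscore of at least 2 (Protocol 5.1, criteria 3 and 4).
- **Use of baseline severity elsewhere.** The ANCOVA for continuous endpoints is fitted "with treatment group, corticosteroid use at baseline (yes, no), and baseline score as the explanatory factors" (SAP 5.5.3), and the MMRM also includes the baseline score. Week 0 Mayo subscores enter the imputation model (SAP Table 3). Baseline Mayo category and endoscopy subscore 2 versus 3 are planned subgroups (SAP 2.3).
- **Sizing.** "A sample size of 210 participants (70 per intervention group") was chosen for a "1-sided chi-square test with 0.1 significance level for each comparison" (Protocol 9.2), so that the "combination therapy has approximately 80% power (based on simulations) to achieve both comparisons to monotherapy for the primary endpoint" (SAP 1.4). SAP 5.2.1 restates the level: "A 2-sided significance level of 0.2 (equivalent to the 1-sided 0.1 level specified in the protocol").
- **Interim.** An analysis of the first 126 participants took place in April 2020, with a limited number of sponsor personnel unblinded to those data (SAP 1.2, 1.5).

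**The concern.** Response and remission are both built from the Mayo score, and its baseline value is recorded before dosing for essentially every participant. The SAP adjusts for baseline score when the outcome is a change in Mayo score, but not when the same score is turned into the two headline binary outcomes. If baseline severity predicts those outcomes, any chance imbalance in severity between arms stays in the reported risk difference, and the interval is somewhat wider than it need be. What is at stake is the precision of the two effect estimates that a reader of a proof-of-concept trial will look at first.

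**Working it through.** 1. **Inputs.** From the documents: 70 per arm, "randomized in a 1:1:1 ratio"; response 55%, 55% and 75%; one-sided 0.1, which is the same as two-sided 0.2, so z = 1.2816. Assumed, because the documents are silent: the prognostic strength of baseline severity and the share of participants with endoscopy subscore 3.

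2. **The plan's own power.** Take three independent Binomial(70, p) arms with a shared combination arm. Reject when (p_c - p_m) / sqrt(2·p̄(1 - p̄)/70) ≥ 1.2816. Joint power is the sum over x of P(X_c = x) · P(beat golimumab | x) · P(beat guselkumab | x). The six rows of SAP Table 1 come out at 79.2, 65.8, 69.1, 81.4, 89.9 and 85.4%, against the stated 79, 66, 69, 81, 90 and 85%. A simulated CMH stratified by corticosteroid use (equal strata and no corticosteroid effect, both assumed) gives about 81% at 55/55/75. The planned test delivers the planned power.

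3. **Planned interval width.** Half-width = 1.2816 · sqrt((0.75·0.25 + 0.55·0.45)/70) = 1.2816 · sqrt(0.435/70) = 10.1 points.

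4. **What adjustment could change.** A standardised logistic risk difference with a degrees-of-freedom-corrected standard error was simulated (3000 trials, 70 per arm, assumed covariates). The last column is 10.1 times the square root of the variance ratio.

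| Prognostic effect (assumed) | Change in variance | 80% half-width |
|---|---|---|
| None | about +1 to +3% | 10.15 to 10.25 |
| Weak | about 0% | 10.1 |
| Strong | about -7 to -8% | 9.74 to 9.69 |

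   Coverage of the adjusted 80% interval was 78 to 80%, and one-sided error was 10.2 to 10.6%. In a separate run of 6000 trials without the correction, the standard error was about 2 to 5% too small, coverage about 78 to 79% and one-sided error 10.8 to 11.2%. The correction is therefore needed.

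5. **What strong means.** For endoscopy subscore alone, the share of outcome variance explained is about R² = gap² · q(1 - q) / (0.65·0.35). Here gap is the difference in response rate between subscores 2 and 3, q is the share with subscore 3, and 0.65 is the mean of 75% and 55%. With q = 0.5, gaps of 10, 20, 25 and 30 points give R² = 0.011, 0.044, 0.069 and 0.099. A net saving of 7 to 8% therefore needs a gap of roughly 25 to 30 points. The 1 to 3% cost is recovered only at a gap of roughly 10 to 17 points, since sqrt(0.01·0.2275/0.25) = 0.095 and sqrt(0.03·0.2275/0.25) = 0.165.

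6. **Chance imbalance.** If 60% have subscore 3, the difference in that share between two arms has SD sqrt(2·0.6·0.4/70) = 8.3 points. With a 20-point gap, a one-SD imbalance moves the risk difference by 0.083 · 20 = 1.7 points.

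7. **Which endpoint.** Remission is an absolute threshold (Mayo score at most 2, no subscore above 1). A participant at Mayo 12 must fall 10 points and one at Mayo 6 must fall 4; endoscopy 3 must fall two grades and endoscopy 2 only one. Response is relative to the participant's own baseline. The required fall is 3 points for baselines 6 to 10 and 4 points for 11 and 12 (30% of 11 is 3.3, and of 12 is 3.6). A prognostic link is built into the definition of remission but not into that of response. The documents give no remission rates by arm, so no size is attached to remission.

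**The case against.** A reader might infer that the plan throws away power, or that the primary test is deficient. The documents do not support that. The CMH test respects the only randomisation stratum, is the test fixed in Protocol 9.4.1.2 and 9.4.1.3, and reaches the stated joint power without further adjustment. No document links baseline Mayo score or endoscopy subscore to Week 12 outcome, and the gain is nil if there is no link. For response even the direction is unclear: entry restricts the range, a higher baseline leaves more room to fall, and baselines of 11 and 12 demand a larger fall. Baseline severity is also not ignored overall. It is tabulated by arm, examined in subgroups, and adjusted for in the analysis of Mayo change. Finally, choosing covariates after an unblinded interim look could seem data-driven.

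All of this stands, and it limits the point to the effect estimate. It does not remove the point: the reported difference states no adjustment at all, the covariates are already collected, and the cost if they prove uninformative is small. The interim look is a reason to settle who chooses the covariates and when, not a reason to leave the estimate unadjusted.

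**Conclusion.** The point holds as a missed efficiency of modest and unknown size in the reported risk differences. At best, under a strong assumed prognostic effect, the variance falls by about 7 to 8% and the half-width by about 0.4 points out of 10.1. With no prognostic effect the variance rises by about 1 to 3%. The gain is most plausible for remission. No gain in power should be claimed, because the chance of declaring success does not change while the CMH rule stands. The sizes rest on assumed prognostic strengths and covariate distributions, on 70 per arm, and, for the interval widths, on response rates of 75% against 55%.

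**What to change.** In SAP 5.3.3.1 and 5.4.3.1, keep the CMH test and the success rule as they are. For each endpoint and each comparison, add a covariate-adjusted effect estimate and show it beside the unadjusted difference:

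- Fit a logistic model with treatment, corticosteroid use, baseline Mayo score and baseline endoscopy subscore (2 versus 3).
- Predict each participant's probability under both treatments, average over both arms, and take the difference. This keeps the difference in proportions that SAP 5.3.2 names as the summary measure; an odds ratio would not.
- Give a robust 80% interval with a small-sample (degrees-of-freedom) correction.

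Staff still blinded to the interim data should fix the model and covariates before the Week 12 lock, and the SAP should say so.

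The cost is one SAP paragraph and a few lines of code. There are two downsides: about 1 to 3% more variance if the covariates are not prognostic, and an adjusted interval that may occasionally disagree with the CMH test at the margin. The SAP should state that the CMH test decides success in that case.
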